3.1.6 Adverse Event Reporting Requirements

Each subject will be evaluated for the development of AEs. It is the responsibility of the investigator to document all AEs occurring during this investigation, whether or not the AE is considered drug-related. All AEs will be reported to the Sponsor via the CRF. Non-serious AEs will be reported from study drug administration through hospital discharge. SAEs will be reported from study drug administration through study completion (Day 90 visit or early termination). SAEs require expedited review and will be reported by the site to the Sponsor or designee by telephone or electronically within 24 hours of discovery. The nature of each event, date and time of onset, outcome, frequency, intensity, action taken with respect to dosage, whether it was serious or non-serious, and relationship to treatment should be documented. Signs and symptoms should be grouped into a single diagnosis and reported as a single AE when appropriate. SAEs should be followed by the investigator to resolution, or, if the SAE is not expected to resolve, it should be followed until stabilization.

AEs should be documented in terms of a medical diagnosis(es) when possible. AEs not previously documented at Baseline as pre-existing conditions will be recorded in the CRF.

The following definitions will be utilized when classifying AEs:

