2.7 Randomization

This protocol is using the step-forward, pre-encounter method of randomization that has been developed for rapid availability of research study agents in emergency trials. Each ambulance will be carrying only one study kit at any time, the next kit in its permuted random block sequence. Randomization will be 1:1 between active TSC and placebo. When that ambulance enrolls a subject, the subject will be assigned to the treatment group of the study agent kit the ambulance is carrying at the time. Subjects will be considered enrolled in the trial upon study drug injection.

A Schedule of Events is included as an Appendix 8.1 to this protocol.

The study design is shown in Table 4.

Table 4. Study Design

On Ambulance Within 2 hours of first stroke symptoms

- Perform mLAPSS
- Determine study eligibility in consultation with PHAST-TSC central enrolling physician
- Explicit informed consent or EFIC enrollment
- Perform GCS; Los Angeles Motor Scale (LAMS); Paramedic Global Impression of Change Score (PGIC)
- Obtain heart rate; blood pressure; body weight estimate
- Administer study drug (TSC or placebo) as IV injection

Emergency Department Arrival

- Informed Consent, if enrolled by EFIC
- SOC demographics; heart rate; blood pressure; body weight; pregnancy screening; labs (hematology, chemistry, coagulation); troponin
- SOC brain imaging done within 48 hours of Emergency Department arrival
- Performs mRS; BI; NIHSS
- tPA dose
- Concomitant medications/therapies
- Adverse events

24 Hours

- Obtain Informed Consent if enrolled by EFIC and not obtained at previous visit
- SOC heart rate; blood pressure; labs (hematology, chemistry, coagulation); troponin
- SOC body weight; pregnancy screening if not obtained during previous visit
- Concomitant medications/therapies
- Adverse events
- Performs NIHSS

48 Hours

- Obtain Informed Consent if enrolled by EFIC and not obtained at previous visit
- SOC heart rate; blood pressure; labs (hematology, chemistry, coagulation); troponin
- Concomitant medications/therapies
- Adverse events
- Performs NIHSS

Day 4 (If discharged prior, by phone)

- Obtain Informed Consent if enrolled by EFIC and not obtained at previous visit
- SOC heart rate; blood pressure; labs (hematology, chemistry, coagulation); troponin
- Concomitant medications/therapies
- Adverse events
- Performs mRS; BI; NIHSS

Day of Discharge

- Concomitant medications/therapies
- Adverse events
- Discharge date and destination

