Day 30 (± 6 days) Follow-up (by phone)

To be performed by a Study Coordinator blinded to subject and subject chart:

- Obtain Informed Consent if enrolled by EFIC and not obtained at previous visit
- Concomitant medications/therapies
- Adverse events
- mRS; BI

Day 90 (± 14 days) Follow-up

To be performed by a Study Coordinator blinded to subject and subject chart:

- Obtain Informed Consent if enrolled by EFIC and not obtained at previous visit
- Concomitant medications/therapies
- Adverse events

•

mRS; BI; NIHSS; LAMS; Stroke Impact Scale (SIS-16) Quality of Life Assessment and AMC-Linear Disability Scale (AMC-LDS)

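### Non-serious AE reporting stops at hospital discharge, so its window varies by subject and may differ between arms; the SAE and mortality objectives are unaffected

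*Protocol*

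**What the plan says.** Protocol Section 3.1.6 sets a general duty and then two different windows.

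- General duty: "It is the responsibility of the investigator to document all AEs occurring during this investigation, whether or not the AE is considered drug-related", followed by "All AEs will be reported to the Sponsor via the CRF".
- Non-serious events: "Non-serious AEs will be reported from study drug administration through hospital discharge".
- Serious events: "SAEs will be reported from study drug administration through study completion (Day 90 visit or early termination").

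Table 4 in Section 2.7 lists adverse events, without qualification, at ED arrival, 24 hours, 48 hours, Day 4, day of discharge, Day 30 and Day 90. The Day 4 entry is headed "Day 4 (If discharged prior, by phone"), so the table foresees that some subjects will have left hospital by then. Day 30 is a phone contact. The day-of-discharge entry also records "Discharge date and destination".

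Section 2.3.3 defines the primary safety comparison as SAE frequency by arm. Section 2.3.4 limits the secondary safety objectives to organ-specific classes of SAEs and mortality.

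**The concern.** A window that ends at discharge is not fixed in advance. Its length is settled after randomisation by how the subject fares. Section 2.3.1 sets out to show that TSC reduces disability, so an effect on length of stay is plausible, although the protocol neither names length of stay as an endpoint nor gives data on it.

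If stays are shorter on TSC, fewer non-serious AEs are captured there even when the daily rate is the same in both arms, and the drug looks better tolerated than it is. If TSC lengthens stays, for example by keeping sicker subjects alive in hospital, the distortion runs against it. Either way, a table of subjects with at least one non-serious AE compares unequal observation times.

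There is also a practical gap. A coordinator who phones a discharged subject on Day 4 finds adverse events on the visit list, but under Section 3.1.6 a non-serious event that began after discharge is no longer reportable. Sites could reasonably handle this differently.

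**Working it through.** **The provisions side by side**

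| Contact (Table 4) | Subject's status | Non-serious AEs under 3.1.6 | SAEs under 3.1.6 |
|---|---|---|---|
| ED arrival, 24 h, 48 h | in hospital | reported | reported |
| Day 4 | still in hospital | reported | reported |
| Day 4, by phone | already discharged | stopped at discharge | reported |
| Day of discharge | leaving hospital | last day of reporting | reported |
| Day 30, Day 90 | discharged | stopped at discharge | reported |

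For subjects still in hospital on Day 4, table and rule agree. At Day 30 and Day 90 the adverse-event item has a necessary use, because SAEs are themselves AEs (Section 3.1.2) and must be collected to Day 90. The item does not say that it is restricted to SAEs, so it is ambiguous. The clearest loss is the early-discharged subject at Day 4: the contact takes place and the item is listed, but the reporting rule has already closed.

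**Illustration of size**

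The protocol has no figure to reproduce. Every input below is an assumption:

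- the same constant daily rate L of a first non-serious AE in both arms, 0.10 or 0.15;
- length of stay T of 4 days in one arm and 5 days in the other.

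The share of subjects with at least one captured event is P = 1 − exp(−L × T).

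- L = 0.10: 1 − exp(−0.40) = 33.0% and 1 − exp(−0.50) = 39.3%. The gap is 6.4 points before rounding.
- L = 0.15: 1 − exp(−0.60) = 45.1% and 1 − exp(−0.75) = 52.8%. The gap is 7.6 points.
- Expected event counts are L × T, so their ratio is 4/5 = 0.80, or 20% fewer in the shorter-stay arm at either rate.

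The true difference is zero in each case, so the whole gap comes from the window.

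**How the result moves with the assumptions**

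- *Events cluster early.* Section 2.2 describes a single field bolus with no further study drug in hospital. If no events occurred after day 4, the fifth day would add nothing and the gap would be 0.
- *Stays vary within an arm.* Putting the mean stay m into a concave formula overstates each arm's share. If stays were exponentially distributed, P = Lm/(1 + Lm). At L = 0.10 this gives 0.40/1.40 = 28.6% and 0.50/1.50 = 33.3%, a gap of 4.8 points. At L = 0.15 it gives 0.60/1.60 = 37.5% and 0.75/1.75 = 42.9%, a gap of 5.4 points.
- *Common window.* With 4 days observed in both arms, L = 0.10 gives 33.0% in each and the artificial gap is 0.

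**The case against.** The strongest reply is that no stated safety objective is touched. The primary comparison is SAE frequency, the secondary objectives are SAE classes and mortality, and SAE reporting runs to Day 90 or early termination whether or not the subject has gone home. An event that prolongs hospitalisation is itself serious under Section 3.1.2, so it stays in the longer window. All of this stands, and it confines the point to the descriptive comparison of non-serious events.

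Second, the wording can largely be reconciled. The sentence "It is the responsibility of the investigator to document all AEs occurring during this investigation" is a general duty, and the more specific sentences after it set the windows. A reader might infer that Table 4 flatly contradicts Section 3.1.6 at Day 4, Day 30 and Day 90. The protocol does not support that: Day 4 agrees for anyone still in hospital, and the later items can be read as SAE collection. The Schedule of Events in Appendix 8.1 is not shown and may settle what is asked at each contact. It follows that divergent collection by sites is a risk, not a certainty.

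Third, for a single-dose drug a shorter window for non-serious AEs is a defensible choice. That is also right. The weakness is not that the window is short, but that it is tied to discharge.

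Fourth, the analysis can be left to the SAP. Discharge date and AE onset date and time are recorded, so rates per person-day are available without a protocol change. This stands only in part. Person-day rates assume that risk is roughly constant over the stay, which is doubtful after one bolus. No analysis can recover non-serious events that were never collected between an early discharge and Day 4.

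**Conclusion.** The point holds as a modest weakness in data collection. The discharge rule gives each subject a different window for non-serious AEs, with an end point that treatment may influence, and it leaves unused a Day 4 contact that is already scheduled. The between-arm description of non-serious AEs can be distorted in either direction.

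The size cannot be established from the protocol. The 6 to 8 point gap rests wholly on assumed rates of 0.10 to 0.15 per day, assumed stays of 4 versus 5 days and a constant rate; early clustering or spread in stays makes it smaller. A reader might push the same formula to stays of 4 versus 7 days, where the gaps are 17.4 points (50.3% − 33.0%, before rounding) and 19.9 points (65.0% − 45.1%). Nothing in the protocol supports a stay 75% longer in one arm, so those figures should not be used to judge importance.

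A reader might also infer that the trial's safety conclusion is biased, since Section 2.2 makes safety a primary objective. Sections 2.3.3 and 2.3.4 do not bear that out, because the objectives they define do not depend on discharge.

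**What to change.** In Section 3.1.6, require non-serious AEs to be collected through at least the Day 4 contact for every subject, by phone if already discharged. Compare arms on the common injection-to-Day-4 window. List non-serious events later in the stay separately, or report them per person-day, because that part of the window still depends on discharge.

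In Table 4, label the Day 30 and Day 90 items as SAEs so that they match Section 3.1.6, and check Appendix 8.1 for the same wording. Extending non-serious AEs to those two contacts would be the more expensive route: Table 4 assigns them to a coordinator blinded to the subject's chart, who could not readily separate new events from pre-existing conditions.

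The cost is a change of wording in two places and a few extra non-serious AEs recorded at a call that already exists, with no new visit or staff. Two limits remain. Ascertainment to Day 4 would be by phone for discharged subjects and direct for inpatients, so some dependence on discharge persists. Death before Day 4 still shortens the window, but deaths are reported as SAEs.

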3.1.6.1 Severity

- Mild: Awareness of signs or symptoms, but easily tolerated and are of minor irritant type causing no loss of time from normal activities. Symptoms do not require therapy or a medical evaluation; signs and symptoms are transient.
- Moderate: Events introduce a low level of inconvenience or concern to the participant and may interfere with daily activities but are usually improved by simple therapeutic measures; moderate experiences may cause some interference with functioning.
- Severe: Events interrupt the participant's normal daily activities and generally require systemic drug therapy or other treatment; they are usually incapacitating.

3.1.6.2 Relatedness

- Unlikely or Not Related: The adverse event is doubtfully related or clearly not related to the investigational agent/procedure i.e. another cause of the event is most plausible; and\or a clinically plausible temporal sequence is inconsistent with the onset of the event and the study intervention and/or a causal relationship is considered biologically implausible.
- Possibly Related: The adverse event may be related to the investigational agent/procedure i.e. an event that follows a reasonable temporal sequence from administration of the study intervention, follows a known or expected response pattern to the suspected intervention, but that could readily have been produced by a number of other factors.
- Probably Related: The adverse event is likely related to the investigational agent/procedure i.e. an event that follows a reasonable temporal sequence from administration of the study intervention, follows a known or expected response pattern to the suspected intervention, that is confirmed by improvement on stopping and is unlikely to be attributed to the known characteristics of the subject's clinical state.
- Definitely related: The adverse event is clearly related to the investigational agent/procedure i.e. an event that follows a reasonable temporal sequence from administration of the study intervention, follows a known or expected response pattern to the suspected intervention, that is confirmed by improvement on stopping and that could not be reasonably explained by the known characteristics of the subject's clinical state.
